## Twenty-Four-Month Clinical Comparison of Two Bulk-Fill and Microhybrid Composite Restorations

### Materials and Methods

#### Patient selection

The Research Ethics Committee of Tokat Gaziosmanpasa University (Tokat, Turkey) approved the study, and a group of patients who were seeking routine dental care was subsequently recruited by the Department of Restorative Dentistry, Faculty of Dentistry, Tokat Gaziosmanpasa University, and screened for inclusion in the study. A total of 25 patients who needed at least three similar Class II restorations were asked to participate in the study.

The inclusion criteria were as follows: Patient in need of restoration of caries lesion (diagnosed with bitewing radiograph and clinical examination); teeth in need of restoration to be first or second molars or permanent premolars; at least three Class II restorations required in each patient and the number of restorations of each material to be equal in each patient; the antagonist and adjacent tooth in contact; pulp vitalized and free of painful symptoms; teeth involved not to have undergone direct pulp capping; no history of hypersensitivity in the teeth to be restored; permanent dentition; good oral health and absence of periodontal disease; patients not to have suffered from systemic diseases or allergies; and absence of deleterious habits, xerostomia, and bruxism.

Specific exclusion criteria were as follows: Fewer than 20 teeth; history of existing tooth sensitivity; known allergy to resin-based materials or any of the other materials used in this study; pregnancy or breastfeeding; chronic use of anti-inflammatory drugs, analgesic, and/or psychotropic drugs; non-vital teeth; abutment teeth for fixed or removable prostheses. The average age of patients was 20 years (range, 18–22 years). All patients participated voluntarily and were required to provide written informed consent. The purpose and implications of the treatment were discussed with the patients, and all participants consented to participate voluntarily in the study by signing a term of informed consent. The participants were informed that they were free to withdraw from the trial without justification at any stage of the research.

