The dental cavities were at least 3 mm deep. A bitewing radiograph of each tooth was taken using an X-ray device. The operator measured the height and depth of the proximal and occlusal cavity boxes with a periodontal probe (Satin Steel Handle; mm, Hu-Friedy, Chicago, IL, USA). One experienced dentist placed all 75 restorations. The filling materials and adhesives (**Table 1**), bulk fill materials [Sonic Fill (Kerr), x-tra fil (VOCO)] or microhybrid composite (Filtek Z-250 3M ESPE), were used according to the manufacturer's instructions and were randomized over these two cavity groups by using a table of random numbers. Before treatment, initial periapical radiographs of the teeth to be treated were taken and vitality test scores were recorded.

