#### Restorative procedure

All restorations (25 for each restorative material) were performed by the same operator to ensure consistency ([name]). Twenty-five patients received a total of 75 restorations. As such, each patient received three Class II restorations randomly: one with Sonic Fill (Kerr); a conventional viscosity composite, Filtek Z-250 (3M ESPE);

and the other with x-tra fil (VOCO), a high-viscosity bulk-fill composite. Local anesthesia was applied for patients who complained of pain or sensitivity. The cavity preparation was made by using a spherical diamond bur (Meisinger Dental Burs, Hager and Meisinger GmbH, Neuss, Germany) on a high-speed air turbine. Infected dentin in the cavity was removed by carbide round burs used with a low-speed handpiece, and no bevel was prepared. Discolored but hard dentine was left in place at the cavity floor. The cavities were designed according to the principles of minimally invasive dentistry. None of the cavity preparations involved one or more cusps. All of the gingival margins included sound enamel. The operative field was cleaned with an air/water spray, gently air-dried, and then carefully isolated with cotton rolls and suction. The outline shape of the preparations was limited to the removal of caries; as such, no additional retention and bevel was prepared. For each restoration, the tooth type (molar/premolar) and cavity type (number of restored surfaces) were recorded. All patients received oral hygiene instructions and a professional tooth cleaning before initiating the restorative intervention. No liner or base was used.

An ivory type matrix system (Hahnenkratt, Königsbach-Stein, Germany) and wooden wedges were used. To remove water, the cavities were rinsed for 10 s and air-dried for 5 s. Three adhesive systems were used: OptiBond™ XTR (Kerr), Solobond M (VOCO), Adper Single Bond 2 (3M ESPE). The adhesives were applied following the manufacturer's instructions (**Table 1**). All light-curing procedures were performed with the same LED-curing unit (Model BUILT-IN C, Guilin Woodpecker Medical Instrument Co., Ltd., Guilin, Guangxi, China) operating in a continuous mode while emitting a light-intensity of 1200 mW/cm^2 according to the manufacturers' recommended polymerization times. The light was directed perpendicular to the occlusal surface.

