Three different restorative resins were placed in each patient, resulting in a total of 75 restorations; 25 of the preparations were restored using the bulk-fill resin composite Sonic Fill (Kerr, Orange, CA, USA) (n = 25), 25 of them were restored with Filtek Z-250 (3M ESPE, St Paul, MN, USA) (n = 25), and 25 of them were restored with x-tra fil (VOCO, Cuxhaven, Germany), according to the manufacturers' instructions (**Table 1**). The Filtek Z-250 restorative material was applied using an incremental filling technique, beginning at the gingival wall. The increments, not exceeding 2 mm in thickness, were added to complete the proper anatomical form. Each increment was polymerized for 20 seconds. The x-tra fil restorative material was placed in bulk up to 4 mm in thickness and cured for 10 seconds with the same curing unit. The other bulk-fill resin composite material, Sonic Fill, was applied to the bonded cavities with sonication (SonicFill Handpiece, Kerr) and photo-polymerized for 40 s according to the manufacturer's instructions. The randomization of restorative material was done using a table of random numbers.

After removal of the matrix system, the restorations on the teeth in all groups were light-cured for a further 20 s from the buccal, lingual, and occlusal aspects. The cotton rolls were then removed, and occlusion and articulation were checked and adjusted. The surface of the teeth was finished with fine-grit diamond instruments (Diatech, Coltene, Switzerland), polishing disks (Sof-Lex, 3M-ESPE, MN, USA), and rubber polishing instruments (One Gloss, Shofu, Kyoto, Japan). Water-cooling was used throughout the finishing procedures. We used abrasive strips (3M ESPE, St. Paul, MN, USA) on the proximal surfaces when necessary. We checked the quality of the interproximal contact and the cervical adaptation by means of dental flossing and bitewing radiographs. The clinical procedure of tooth preparation and placement of restorations was performed by the same operator.

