### **Periods and evaluation criteria**

One week after restoration placement (baseline), patients were recalled and restorations were examined clinically. Direct clinical evaluation of restorations was performed using the USPHS criteria (**Table 2**) by two independent investigators ([name] and [name]) using mirrors, probes, and bitewing radiographs and scored as Alpha, Bravo, or Charlie. Alpha corresponded to excellent, Bravo to clinically acceptable, and Charlie to clinically unacceptable results (**Table 2**). Patients were recalled at 6, 12, and 24 months for assessments of the restorations, using the same criteria as at baseline. At each recall, the same two calibrated evaluators, who were blinded to the restoratives used for cavities and patients, examined the restorations. To ensure a double-blind study, the evaluators were not informed about which filling material had been used on which teeth. When disagreement occurred during the evaluation, the final decision was made by the consensus of both examiners. All evaluations were carried out under a dental operating light, using flat-surfaced mouth mirrors and dental explorers. Postoperative sensitivity was assessed by blowing a stream of compressed air for three seconds at a distance of 2 to 3 cm from the restoration under isolation from the adjacent teeth with gauze and by moving the probe over the restored tooth surface.

The statistical analyses were carried out with the IBM SPSS version 22.0 software package (SPSS, Chicago, IL, USA). The restoration groups for each category were compared using the Pearson chi-square test, and the Cochran Q-test was used to compare the changes across different time points within each restorative material ( $p < 0.05$ ).

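### Materials are tested category by category at 0.05 each, with no primary outcome or visit, no multiplicity control and no exploratory label, so the chance of a false material difference is not held at 5%

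*Combined protocol and SAP*

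**What the plan says.** The statistical plan is the closing paragraph of the section Periods and evaluation criteria. For the comparison of materials it says: "The restoration groups for each category were compared using the Pearson chi-square test". A second family of tests concerns time: the "Cochran Q-test was used to compare the changes across different time points within each restorative material". A threshold of 0.05 is given once.

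On timing, the same section has a baseline examination one week after placement, and then: "Patients were recalled at 6, 12, and 24 months for assessments of the restorations, using the same criteria as at baseline". That makes four assessments. The text does not say at which of them the chi-square test is run; 24 months only and all four visits are both possible readings.

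On design, Restorative procedure states: "Three different restorative resins were placed in each patient, resulting in a total of 75 restorations". Each of the 25 patients therefore contributes one restoration per material.

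No section names a primary category, a primary visit, a primary contrast between materials, a study-wide error rate or an adjustment for multiple tests. No section describes the comparisons as exploratory.

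**The concern.** When several categories are each tested at 0.05, the materials can be declared different on whichever one crosses the threshold, and at whichever visit if all visits are tested. A reader would take p < 0.05 as a 5% risk of a false claim about the materials. The plan holds that risk for one test only.

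The time tests within each material answer a different question and are not counted here.

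**Working it through.** **The plan's own figure.** There is none to reproduce: no study-wide error rate and no sample-size calculation are given.

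**Inputs from the documents.** 25 restorations per material, three materials in every patient, threshold 0.05, and four assessments (one week, 6, 12 and 24 months).

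**Assumptions.** The number of categories is taken as 5 to 8, because the body of Table 2 is not in the text available for this review; that gap is not held against the plan. Scores are collapsed to Alpha versus non-Alpha, giving a 3×2 table with 2 df. Categories are independent, a non-Alpha score persists, no patient is lost, and the materials are truly identical. Within-patient correlation, on a latent scale, is 0 to 0.5. The non-Alpha rate at 24 months is varied.

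**Step 1: nominal rate.** For k independent tests at 0.05 the chance of at least one false positive is 1 − 0.95^k, which is 22.6% for k = 5 and 33.7% for k = 8.

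**Step 2: actual size of one test.** With 25 per material, Pearson's test falls short of 5% when events are sparse. At least 3 non-Alpha scores among the 75 restorations are needed before it can reject. Enumerating all 3×2 tables with independent restorations, and then applying 1 − (1 − size)^k:

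| Non-Alpha | Size of one test | k = 5 | k = 8 |
|---|---|---|---|
| 1% | 0.0035 | 1.7% | 2.8% |
| 2% | 0.0146 | 7.1% | 11.1% |
| 5% | 0.0350 | 16.3% | 24.8% |
| 20% | 0.0468 | 21.3% | 31.8% |

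**Step 3: patients receiving all three materials.** The null was simulated with 20,000 trials per cell. Rates rise over the visits to the value shown. Each range covers 5 to 8 categories and correlation 0 to 0.5.

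| Non-Alpha at 24 months | 24 months only | All four visits |
|---|---|---|
| 0.5% | 0.2–0.5% | 0.2–0.5% |
| 1% | 0.9–2.7% | 1.0–2.9% |
| 2% | 3.4–11.0% | 4.2–12.3% |
| 5% | 8.1–24.5% | 13.2–36.2% |
| 10% | 7.2–24.6% | 18.2–47.1% |
| 20% | 7.2–31.8% | 21.7–58.7% |
| 30% | 6.5–33.8% | 20.5–62.8% |

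**Step 4: outside that grid.**
- Correlation 0.7, 5 categories, 24 months only, 5 to 30% non-Alpha: about 2 to 4%.
- Two or three categories, 10 to 30% non-Alpha: 2.6 to 14% at 24 months only, and 8 to 31% at all visits.
- A different visit model (7 categories, the same rate at each visit, between-visit correlation 0.8, between-category correlation 0.3), all four visits, at within-patient correlation 0 / 0.3 / 0.5: 7.7 / 6.8 / 4.8% at 1% non-Alpha, and 57 / 47 / 35% at 5%.

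**Step 5: a paired test without adjustment.** Replacing Pearson by Cochran's Q across materials, with 10 to 30% non-Alpha and 5 to 8 categories, gives 20 to 34% at 24 months only and 33 to 70% at all visits.

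**The case against.** The strongest reply is that the inflation may not occur. Three things can hold the error down.

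- **Rarity.** Low non-Alpha rates are plausible here. Patient selection requires "absence of deleterious habits, xerostomia, and bruxism", and Restorative procedure reports "All of the gingival margins included sound enamel" and no cusp involvement. At about 1% non-Alpha and a single visit, the error stays below 5%.
- **Correlation.** Pearson's test ignores that each patient received all three materials. Positive within-patient correlation then makes every test conservative.
- **Few categories.** With two or three, the single-visit error can be under 5% even at 10 to 30% non-Alpha.

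All of this stands. A reader might infer that the error exceeds 5% unless non-Alpha scores are very rare, or that it always does so from 5% non-Alpha upwards. The documents support neither: both readings depend on stopping at correlation 0.5 and at 5 categories, limits found nowhere in the plan. Nor does the text establish that all four visits are tested. The all-visit figures also depend on the model, as step 4 shows, so no sharp boundary should be read from them. A Pearson test on all three grades is another possible reading, and it was not simulated.

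What does not stand is the conclusion that nothing need change. None of these protections is planned. The one from correlation comes from using a test that does not match the design, and it disappears once a paired test is used without adjustment (step 5). A defence that the study is small and exploratory would need the plan to say so. The title presents a clinical comparison of materials, and no section limits its status.

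**Conclusion.** The point holds as a gap in error control. The plan tests several categories at 0.05 each, with no primary category or visit, no multiplicity procedure and no exploratory label, so the chance of at least one false material difference is not controlled at 5%. This much follows from the text alone.

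The size does not. Under the assumptions listed, with 5 to 30% non-Alpha at 24 months and correlation up to 0.5, it is about 6.5 to 34% for a single 24-month analysis and 13 to 63% over four visits. Other plausible settings put it below 5%. The supportable statement is that the error can be well above 5%, depending on the non-Alpha rate, number of categories, visits tested and within-patient correlation. It cannot be said that the error must be above 5%.

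The sponsor should correct this. It does not invalidate the data.

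**What to change.** **If results by material have not been seen.** Name one 24-month primary outcome per restoration, as Alpha versus not: either one named USPHS category on which non-Alpha scores are expected, or the worst grade across categories. If each of 5 to 8 independent categories has 5% non-Alpha, the worst grade is non-Alpha in 1 − 0.95^5 = 22.6% to 1 − 0.95^8 = 33.7% of restorations. Test Sonic Fill against Filtek Z-250, and x-tra fil against Filtek Z-250, within patient (for example exact McNemar), with Holm over the two. The paired test is chosen because Pearson ignores the pairing, and the two contrasts because a three-group test cannot say which bulk-fill differs. Report all other categories and visits as exploratory estimates with 95% confidence intervals.

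The grade described as "Charlie to clinically unacceptable results" makes a poor primary endpoint for these tests. Holm's first step is 0.05/2 = 0.025. Exact McNemar gives 2 × 0.5^6 = 0.031 for a 6–0 split and 2 × 0.5^7 = 0.016 for 7–0, so at least 7 discordant pairs of 25, all one way, are needed.

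**If results have been seen.** This is possible, since the text is in the past tense ("One experienced dentist placed all 75 restorations"). A primary can then no longer be designated. State how many between-material tests were run, apply Holm over all of them using a within-patient test (for example Cochran's Q across the three materials), and label unadjusted results exploratory.

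**Cost.** No new data: plan wording in the first case, re-analysis and labelling in the second. Isolated results with p < 0.05 become descriptive, and with 25 patients only large differences are detectable. For the two McNemar contrasts, power per contrast is about 16 to 21% for a 20-point difference in non-Alpha and 63 to 86% for 40 points, with familywise error at most 2.4%. For Holm over 5 to 32 Cochran Q tests, power for one category is 5 to 30% and 37 to 92%, with familywise error at most 4.1%; by itself this gives no pairwise answer.

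### Materials are compared only by Pearson chi-square, which ignores the within-patient design and gives unreliable p-values, in either direction, when scores are sparse

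*Combined protocol and SAP*

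**What the plan says.** The statistical paragraph that closes the section on periods and evaluation criteria gives one rule for comparing materials: "The restoration groups for each category were compared using the Pearson chi-square test". The level is 0.05. No exact or Monte Carlo option is mentioned, and there is no rule for small expected counts. A repeated-measures test does appear, but only for time: "the Cochran Q-test was used to compare the changes across different time points within each restorative material".

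The design is within-patient. The section on the restorative procedure states that "each patient received three Class II restorations randomly", that "Three different restorative resins were placed in each patient, resulting in a total of 75 restorations", and that "The randomization of restorative material was done using a table of random numbers".

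The outcome has three ordered scores: "Alpha corresponded to excellent, Bravo to clinically acceptable, and Charlie to clinically unacceptable results".

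**The concern.** The Pearson chi-square treats the 75 restorations as three independent samples of 25 and takes its p-value from a large-sample curve. Neither suits this trial. The three restorations in a mouth share a patient, and with 25 per material a category with few Bravo or Charlie scores gives a very sparse table.

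In such a table a handful of restorations decides which side of 0.05 the result falls on. If the p-value is wrong there, one material may be called worse on evidence that does not support it, or a real difference may be missed. Random assignment of materials within each patient supplies a reference distribution that needs no large-sample argument, and the stated method does not use it.

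**Working it through.** **Inputs.** "Twenty-five patients received a total of 75 restorations", with 25 per material and one of each per patient (restorative procedure section): 25 × 3 = 75, as stated. The level is 0.05 (statistical paragraph). The documents give no score counts, so the splits below are assumed, with all 75 restorations scored and only two score levels observed unless noted. An event is a restoration with the less frequent score.

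**Formulas.** For event counts a/b/c with total m, the expected count per material is E = m/3. Then X² = Σ(count − E)² × [1/E + 1/(25 − E)] on 2 df, and p = exp(−X²/2). The within-patient exact p-value is the share of equally likely within-patient assignments of scores to materials with X² at least as large as observed.

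**Pearson too small**

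- 3/0/0: E = 1, X² = (4 + 1 + 1) × (1 + 1/24) = 6.25, p = exp(−3.125) = 0.044. Three events in one material must lie in three patients, so there are 3³ = 27 assignments. Three of them put all events in one material, so exact p = 3/27 = 0.111. The exact test for independent samples gives 3 × C(25,3)/C(75,3) = 0.102.
- 5/1/0, separate patients: X² = 7.609, p = 0.022; exact 39/729 = 0.053.
- 6/1/1, separate patients: X² = 6.996, p = 0.030; exact 387/6561 = 0.059.

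**Pearson too large**

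- 4/4/0, both events in the same four patients: E = 8/3, Σ(count − E)² = 1.778 + 1.778 + 7.111 = 10.667, and X² = 10.667 × (0.375 + 0.04478) = 4.478, p = 0.107. Each of the four patients has three possible assignments, 3⁴ = 81 in all. Three are as extreme, so exact p = 3/81 = 0.037.
- Three levels, three Charlies and one Bravo all in one material, separate patients: X² = 8.451 on 4 df, p = 0.076; exact 3/81 = 0.037.

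**No change of verdict**

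- 4/0/0: Pearson 0.015, exact 3/81 = 0.037.
- Three levels, three Charlies in one material and two Bravos in every material: X² = 6.273 on 4 df, Pearson 0.18, so Pearson shows no false positive.

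**Size of the nominal 5% Pearson test.** With independent scores, enumerating all splits for a given event total gives 0% at 2 events, 10.2% at 3, between 0.9% and 5.5% at 4 to 14, and 7.5% at 15. Averaged over totals it is 1.5%, 3.5%, 3.5% and 4.7% at common event rates of 2%, 5%, 10% and 20%. With an assumed within-patient correlation of 0.3 (beta-binomial simulation), it falls to about 0.3%, 1.1%, 1.1% and 1.4%.

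**Large-sample Cochran Q across materials.** For 3/0/0, Q = 2 × (3 × 9 − 9)/(9 − 3) = 6, p = exp(−3) = 0.0498, still below 0.05 against exact 0.111. For 4/1/0 with one patient holding two events, Q = 2 × (3 × 17 − 25)/(15 − 7) = 6.5, p = 0.039 against exact 6/81 = 0.074. Pairing alone does not repair the approximation.

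**The case against.** The strongest reply is that 3/0/0 is a selected table. With one common event rate and independent scores, it arises in any one material in only about 1.3%, 2.1% and 0.4% of tables at rates of 2%, 5% and 10%. The verdict does not change at 4/0/0, and that false positive needs a category with only two observed scores. All of this stands, and the table is used here only as an illustration.

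A reader might infer that the plan inflates false positives in general. The documents do not support that. Averaged size is below 5% with independent scores and far below it when scores correlate within patient, in which case Pearson more often misses differences than invents them.

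A reader might also infer that a result of this trial is wrong. No counts are given, so that cannot be said.

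Nor does the usual expected-count warning mark the trouble. At 15 events the expected count is exactly 5, yet the size is 7.5%, higher than at any total from 4 to 14.

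Two further points stand in part. The statistical paragraph names the statistic but not how its p-value was obtained; if an exact option was used, a sentence saying so would settle the approximation but not the neglected pairing. And permutation is only as valid as the allocation it mimics. The last paragraph under patient selection says materials were randomised over two cavity groups that it does not define, so unrestricted assignment within patient needs confirming.

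**Conclusion.** The concern holds as a weakness of the stated test in sparse tables, in both directions. The Pearson p-value ignores the within-patient design, and at small event totals it can cross 0.05 wrongly: 0.044 against 0.111 for 3/0/0, 0.022 against 0.053 for 5/1/0, and 0.107 against 0.037 for 4/4/0.

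It is worth correcting because the remedy is cheap and rests on the trial's own randomisation, not because error rates are shown to be inflated overall. The conclusion assumes that the large-sample p-value was used, that materials were assigned without restriction among a patient's three teeth, and, for the figures, that all 75 restorations were scored. Equal loss to between 20 and 24 restorations per material leaves the 3/0/0 Pearson value at 0.043 to 0.044. Whether any reported comparison is affected can be settled only from the scores.

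**What to change.** Keep the Pearson statistic and the same set of comparisons. Take each between-material p-value from exact or Monte Carlo permutation of the scores within patient. With 9,999 permutations, the standard error at p = 0.05 is √(0.05 × 0.95/9999) ≈ 0.002. For two-level scores with complete data this equals the exact Cochran Q across materials. Do not substitute large-sample Cochran Q, and add no pairwise or failure-only tests without a multiplicity rule.

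Two details must be written down:

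- For a patient with a missing restoration, permute only among the materials that were scored.
- State whether allocation was unrestricted within patient. If it was tied to the cavity groups, permute within that restriction.

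The text is in the past tense, so this is a re-analysis of existing scores. It needs no new data, one changed sentence plus these two rules, and little computing time. The price is that some p-values rise and others fall, so significance may be lost or gained after the fact; report both sets. The exact test is also conservative: with independent scores its size averages about 0.2%, 1.1%, 2.6% and 3.6% at rates of 2%, 5%, 10% and 20%, and no result that rests on three events can reach 0.05.

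### Does the lack of a rule for restorations already rated Charlie make the 24-month failure results wrong?

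*Combined protocol and SAP*

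**What the plan says.** Under Restorative procedure, "Three different restorative resins were placed in each patient, resulting in a total of 75 restorations", and "All restorations (25 for each restorative material) were performed by the same operator". Each material therefore has a known denominator of 25, with one restoration of each material per patient.

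Under Periods and evaluation criteria the scale is defined: "Alpha corresponded to excellent, Bravo to clinically acceptable, and Charlie to clinically unacceptable results". Follow-up is then set: "Patients were recalled at 6, 12, and 24 months for assessments of the restorations, using the same criteria as at baseline".

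The whole analysis consists of two tests at the 0.05 level. Between materials, "The restoration groups for each category were compared using the Pearson chi-square test". Over time, "the Cochran Q-test was used to compare the changes across different time points within each restorative material".

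The text does not define failure, survival or success as a summary outcome. It does not say whether a Charlie restoration stays in place, nor whether its grade is carried to later visits. Table 2, cited there for the criteria, was not in the text available for this check, so a rule there cannot be excluded.

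**The concern.** Charlie is the only unacceptable grade, and a restoration can reach it well before 24 months. If it is then lost or replaced, the original cannot be scored at the last visit. A 24-month table built from what is still scored would omit it from numerator and denominator alike, so the material with the most early failures would gain most. Cochran Q needs a score at every time point, so the same restoration would also drop out of the over-time test. A reader could then take the 24-month table as the overall failure experience and judge a poorly performing material to be equal to the others.

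**Working it through.** **Plan's own figure.** 25 restorations per material × 3 materials = 75, as stated under Restorative procedure. The documents give no failure counts or expected failure rate, so every count below is an assumption.

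**Effect on the percentage.** For one material let f be the failures before 24 months and g the new failures at 24 months.

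- Cumulative: (f + g)/25
- Shown at 24 months if early failures drop out: g/(25 − f)
- Difference: f(25 − f − g)/[25(25 − f)], which is never negative
- If early failures are instead replaced and the new filling is scored acceptable, the figure shown is g/25 and the difference is exactly f/25, or 4 points per early failure.

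With g = 1 and early failures dropped:

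| f | Cumulative | Shown at 24 months | Difference (points) |
|---|---|---|---|
| 1 | 2/25 = 8% | 1/24 = 4.2% | 3.8 |
| 2 | 3/25 = 12% | 1/23 = 4.3% | 7.7 |
| 3 | 4/25 = 16% | 1/22 = 4.5% | 11.5 |
| 4 | 5/25 = 20% | 1/21 = 4.8% | 15.2 |
| 5 | 6/25 = 24% | 1/20 = 5.0% | 19.0 |

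With f = 0 the two figures agree. The direction is certain once the conditions hold. The size depends wholly on f.

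**Are the failures hidden?** If failed restorations leave the data and tables are made per visit, each failure in a given category is counted once, at the visit where it occurred. Adding the Charlie counts across visits within that category gives f + g, and the denominator of 25 is known. The information is spread over several tables but not lost.

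**Effect on the test between materials** (Pearson, 2 df, no correction).

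- *One material with f early failures, and one failure in every material at 24 months.* Cumulative p is 0.77, 0.42, 0.20 and 0.080 for f = 1 to 4, so the cumulative Pearson test is not significant either.
- *The same with f = 5.* Cumulative 6/25, 1/25, 1/25 gives p = 0.030, and the 24-month table 1/20, 1/25, 1/25 gives p = 0.98. However, for every split of the five failures between 6 and 12 months, one earlier Pearson table is below 0.05. The weakest split, three then two, has p = 0.044 (exact 0.102). An exact matched test on the cumulative counts gives 0.059 to 0.012, depending on which patients share failures.
- *Two failures at 6 months and two at 12 months in one material, none elsewhere.* The visit tables give p = 0.13 and 0.11. Cumulative 4/25, 0/25, 0/25 gives Pearson 0.015 (exact 0.031) and matched Cochran Q 0.018 (exact 0.037). Here a signal is missed.
- *The same with one failure in a second material.* Cumulative 4/25, 1/25, 0/25 gives Pearson 0.062 (exact 0.119). Matched Q gives 0.074 or 0.039 (exact 0.136 or 0.074), depending on whether that failure is in a different patient or the same one.

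**Effect on the over-time test.** Take the two-plus-two pattern and an assumed Charlie/not-Charlie split. With Charlie carried forward the visit totals are 0, 2, 4 and 4, and the four failing restorations contribute 3, 3, 2 and 2 Charlie scores. Then Q = 3 × (4 × 36 − 100)/(4 × 10 − 26) = 132/14 = 9.43, p = 0.024. With the four dropped, nothing varies and Q is undefined. Part of the 9.43 comes from assigned scores rather than observed ones, so carrying forward has its own cost.

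**The case for a change.** The strongest case for a change is that the percentage bias can go only one way. With g = 1, a single early failure roughly halves the figure shown. The remedy would be cheap, since the scores are already collected and the denominator is fixed by design. The test can suffer too. Four early failures and one late in one material, one late in the second and none in the third give p = 0.022 cumulatively against 0.56 among those still scored at 24 months.

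What stands is that the visible text has no counting rule, and that a 24-month table limited to restorations still scored should not be read as cumulative failure.

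The rest is conditional. No passage says that a Charlie restoration is removed or replaced. The recall sentence describes scoring the restorations again by the baseline criteria, and if they stay in place nothing is lost. In the 0.022 against 0.56 example, four early failures all at 6 months would already give p = 0.015 in that visit's table. Only an even split over two visits leaves both early tables above 0.05. A cumulative endpoint is a reasonable preference, but it is a different quantity from the category-by-category description that the plan sets out. If follow-up is already complete, as the past tense suggests, such an endpoint would also be post hoc.

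**Conclusion.** No change to the plan follows. The gap is real but is one of missing detail. The possible understatement is about 4 percentage points per early failure per material. It arises only if tables are made per visit, failed restorations cannot be rescored, their grade is not carried forward, and early failures occur at all. The documents establish none of these. Even then, early failures appear in the 6- or 12-month tables, and a lost significant difference needs a particular pattern that one further failure in another material can undo.

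The plan states no failure percentage that would come out wrong. Its Pearson and Cochran Q analyses correctly describe the restorations scored. An analyst would ordinarily give the number scored per material and visit and note any restoration lost after a Charlie grade, which is enough to prevent misreading. This conclusion assumes that Table 2 contains nothing to the contrary. It does not address whether an unmatched Pearson test suits three restorations within one patient, or how missed recalls are handled; both are separate questions.
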